3.2 DISCUSSION OF TRIAL DESIGN, INCLUDING THE CHOICE OF CONTROL GROUP(S)

For single- and multiple-rising dose trials, the sequential rising dose design described in [Section 3.1](#) is viewed favourably under the provision not to expose the patients involved to undue risks.

Single-blind conditions regarding the patient's treatment (active or placebo) are maintained within each dose group. However, patients and investigators will be aware of the dose of BI 894416 administered. The disadvantage of the trial design is a possible observer bias with regard to the dose-dependent effects; in addition, the sequential dosing of groups could potentially result in time-related effects. However, as such effects are expected to be small relative to the differences between the doses in the broad range investigated, unbiased comparisons between treatments can still be expected.

It is standard in single and multiple rising dose trials to include a placebo group to control for safety, tolerability, [REDACTED] of the trial medication. Each dose group consists of 10 patients, with 8 on active treatment, and 2 on placebo. For data analysis purposes, the placebo control group will include all patients of all dose groups treated with placebo. Eight patients per active treatment group are generally considered to be sufficient for the exploratory evaluation of pharmacokinetics.

3.3 SELECTION OF TRIAL POPULATION

Only male patients will be included in the trial because no data on reproductive toxicology are available at this time and because, until availability of the results of the 26-week Tg.rasH2 carcinogenicity study, study populations are restricted to male patients (see IB [c03536505](#)). It is planned that approximately 80 male patients in total will enter the study. The actual number of patients entered may exceed the total of 80 if additional intermediate or lower doses are tested or if number of patients of a dose group is extended (see Section 3.1).

[REDACTED] In addition, the target patient population may allow for an early clinical read-out of efficacy from the MRD portion e.g. changes in airway resistance (Raw), [REDACTED]

[REDACTED] Assessment of safety in a patient population is considered more relevant for subsequent studies in the development program.

A log of all patients enrolled into the trial (i.e. who have signed informed consent) will be maintained in the ISF irrespective of whether they have been treated with investigational drug or not.

3.3.1 Main diagnosis for trial entry

Outpatients with a history of asthma are eligible for inclusion if they meet all the inclusion criteria ([Section 3.3.2](#)) and none of the exclusion criteria ([Section 3.3.3](#)). Please refer to [Section 8.3.1](#) (Source Documents) for the documentation requirements pertaining to the in- and exclusion criteria.

Patients may participate once in the SRD and once in the MRD portions of the study (for details see [exclusion criterion #13](#)).

3.3.2 Inclusion criteria

Patients will only be included into the trial, if they meet the following criteria:

1. Signed and dated written informed consent in accordance with ICH-GCP and local legislation prior to admission to the trial. Medication washout and medication restrictions according to protocol are allowed only after informed consent is obtained.
2. Male patients aged at least 18 years but not more than 55 years at the time of informed consent.
3. Men able to father a child must be ready and able to use highly effective methods of birth control per ICH M3 (R2) that result in a low failure rate of less than 1% per year when used consistently and correctly. A list of contraception methods meeting these criteria is provided in the patient information.
4. Pre-bronchodilator clinic measured FEV₁ of $\geq 70\%$ of predicted normal at the screening visit (Visit 1). Calculations will be based on Global Lung Function Initiative (GLI) formula ([R15-0845](#)).
5. A diagnosis of asthma, diagnosed by a physician.
6. Patients should be non-smokers or ex-smokers who stopped smoking at least 12 weeks prior to screening and are expected to be able to not smoke for the duration of the study.
7. Patients must be able to perform all trial related procedures including pulmonary function tests, nasal brushings.
8. BMI of 18.5 to 32 kg/m² (incl.)
9. For MRD part: Patients are allowed to be on stable inhaled low dose corticosteroid (please refer to GINA guidelines) for at least 4 weeks prior to screening.

3.3.3 Exclusion criteria

Patients will not be allowed to participate if any of the following general criteria apply:

1. Any finding in the medical examination (including BP, PR, echocardiography and echocardiography stress test or ECG and including the neurological examination) is deviating from normal and judged as clinically relevant by the investigator
2. Repeated measurement of systolic blood pressure outside the range of 90 to 140 mmHg, diastolic blood pressure outside the range of 50 to 90 mmHg, or pulse rate outside the range of 50 to 90 bpm
3. Any laboratory value outside the reference range that the investigator considers to be of clinical relevance

Proprietary confidential information © 2020 Boehringer Ingelheim International GmbH or one or more of its affiliated companies

4. Any evidence of a concomitant disease judged as clinically relevant by the investigator
5. Gastrointestinal, hepatic, renal, respiratory, cardiovascular (stress), metabolic, immunological or hormonal disorders
6. Relevant abnormality on stress echocardiography for those 45 of age and older at screening.
7. Cholecystectomy and/or surgery of the gastrointestinal tract that could interfere with the pharmacokinetics of the trial medication (except appendectomy and simple hernia repair)
8. Diseases of the central nervous system (including but not limited to any kind of seizures or stroke), and other relevant neurological or psychiatric disorders
9. History of relevant orthostatic hypotension, fainting spells, or blackouts
10. Chronic or relevant acute infections
11. History of relevant allergy or hypersensitivity (including allergy to the trial medication or its excipients)
12. Use of drugs within 30 days prior to administration of trial medication that might reasonably influence the results of the trial (incl. QT/QTc interval prolongation)
13. Participation in another trial where an investigational drug other than BI 894416 has been administered within 60 days or 5 half-lives (whichever is greater) prior to planned administration of trial medication, or current participation in another trial involving administration of investigational drug. In case of planned participation in the MRD part in this trial the previous participation in one dose group of the SRD part is allowed if BI 894416 has been administered more than 21 days prior to planned administration of BI 894416 in the MRD part. (Participation in an SRD dose group after the patient has participated in the MRD part is not allowed.)
14. Alcohol abuse (consumption of more than 24 g per day) (please refer to [Appendix 10.5](#))
15. Drug abuse or positive drug screening
16. Blood donation of more than 100 mL within 30 days prior to administration of trial medication or intended donation during the trial
17. Intention to perform excessive physical activities within one week prior to administration of trial medication or during the trial
18. Inability to comply with dietary regimen of trial site
19. A marked baseline prolongation of QT/QTc interval (such as QTc intervals that are repeatedly greater than 450 ms) or any other relevant ECG finding at screening
20. A history of additional risk factors for Torsades de Pointes (such as heart failure, hypokalemia, or family history of Long QT Syndrome)
21. Patient unable or unwilling to comply with study requirements, or has a condition that would not allow safe participation in the study
22. History of relevant neurological disorder affecting the peripheral or central nervous system (this includes, but is not limited to: stroke, epilepsy, inflammatory or atrophic diseases affecting the nervous system, cluster headache or any cancer of the nervous system)*
23. History of immunological disease except allergy not relevant to the trial (such as mild hayfever or dust mite allergy) and except asthma in childhood or adolescence

Proprietary confidential information © 2020 Boehringer Ingelheim International GmbH or one or more of its affiliated companies

24. History of cancer (other than successfully treated basal cell carcinoma)
25. Use of any drug that could reasonably inhibit platelet aggregation or coagulation (e.g. acetylsalicylic acid) within 10 days prior to administration of trial medication, or planned use during the trial or within 7 days after last dose of trial medication.

* Febrile seizures in childhood or adolescence, recovered carpal tunnel syndrome, recovered uncomplicated meningitis, recovered herpes zoster, tension headache, occasional benign tics (e.g. due to stress) or minor para- or dysesthesia (e.g. as a side effect of prior blood withdrawal) do not constitute a history of relevant neurological disorder.

For study restrictions, refer to [Section 4.2.2](#).

3.3.4 Withdrawal of patients from treatment or assessments

Patients may discontinue trial treatment or withdraw consent to trial participation as a whole ('withdrawal of consent') with very different implications; please see [Sections 3.3.4.1](#) and [3.3.4.2](#) below.

If a patient is removed from or withdraws from the trial prior to the first administration of trial medication, at least the basic information of this patient will be entered in the case report form (eCRF). The minimum requirements to enter in eCRF will be listed in an 'eCRF instruction guide'.

At the time of discontinuation, a complete end of trial examination will be performed, if possible, and the information will be recorded in the eCRF.

3.3.4.1 Discontinuation of trial treatment

An individual patient must discontinue trial treatment if:

1. The patient withdraws consent for trial treatment or trial participation, without the need to justify the decision
2. The patient needs to take concomitant drugs that interfere with the investigational product or other trial medication
3. The patient is no longer able to participate for other medical reasons (such as surgery, adverse events (AEs), or diseases)
4. One adverse event of severe intensity or one SAE occurs.
5. The patient shows an elevation of AST and/or ALT ≥ 3 -fold ULN combined with an elevation of total bilirubin ≥ 2 -fold ULN (measured in the same blood sample) and/or needs to be followed up according to the 'DILI checklist' provided in the ISF.
6. The patient experiences an infection with SARS-CoV-2 (as confirmed by PCR testing, see [Section 5.2.4](#)).

In addition to these criteria, the physician may discontinue patients at any time based on his or her clinical judgment.

A patient can also be removed from the trial if eligibility criteria are being violated or if the patient fails to comply with the protocol (for instance, by non-adherence to dietary rules, or non-attendance at study assessments).

Proprietary confidential information © 2020 Boehringer Ingelheim International GmbH or one or more of its affiliated companies

If a patient is removed from or withdraws from the trial prior to administration of trial medication, basic data of this patient will be entered in the case report form (eCRF) or trial database and will not be reported in the clinical trial report (CTR).

If a patient is removed from or withdraws from the trial after first administration of trial medication, this will be documented and the reason for discontinuation must be recorded in the eCRF. In this case, the data will be included in the eCRF/trial database and will be reported in the CTR. At the time of discontinuation a complete end of trial examination will be performed if possible and the information will be recorded in the eCRFs. These discontinuations will be discussed in the CTR.

Even if the trial treatment is discontinued, the patient remains in the trial and, given his agreement, will undergo the procedures for early treatment discontinuation and follow up as outlined in the [Flow Charts](#) and [Section 6.2.3](#).

3.3.4.2 Withdrawal of consent to trial participation

Patients may withdraw their consent to trial participation at any time without the need to justify the decision. If a patient wants to withdraw consent, the investigator should be involved in the discussion with the patient and explain the difference between trial treatment discontinuation and withdrawal of consent to trial participation, as well as explain the options for continued follow up after trial treatment discontinuation, please see [Section 3.3.4.1](#) above.

3.3.4.3 Discontinuation of the trial by the sponsor

Boehringer Ingelheim reserves the right to discontinue the trial overall or at a particular trial site at any time for any of the following reasons:

1. New toxicological findings or serious adverse events invalidate the earlier positive benefit-risk assessment. More specifically, the trial will be terminated if more than 50% of the actively dosed patients at one dose level show drug-related and clinically relevant adverse events of moderate or severe intensity, or if at least one drug-related serious adverse event is reported.
2. The expected enrolment goals overall or at a particular trial site are not met
3. Violation of GCP or the CTP by a trial site or investigator, disturbing the appropriate conduct of the trial

The sponsor decides to discontinue the further development of the investigational product.

3.3.4.4 Discontinuation of the trial –Stopping rules

1. Dose escalation will be stopped as soon as at least 2 patients at one dose level on active drug showed relevant individual QT prolongation, i.e. absolute QT or QTc greater than 500 ms or a QTc increase of greater 60 ms from baseline, which has been confirmed by a repeat ECG recording.
2. Dose escalation in the respective trial part will be stopped if the estimated systemic exposure of the next dose level is expected to exceed C_{max} of 5233 nM (group gMean values), AUC_{0-24} of 36,150 nM·h, (group gMean values) or 63,000 nM·h (for the 95th

Proprietary confidential information © 2020 Boehringer Ingelheim International GmbH or one or more of its affiliated companies

percentile of any given patient in the next dose group). In this case, an interim dose level lower than the planned next dose level may be given, or the highest dose group of the SRD and/or MRD part may be reduced, or additional patients may be entered in the current dose group, as long as the expected systemic exposure is not expected to exceed the above mentioned levels. Alternatively, the next dose level may be given if the previous dose levels are deemed safe after thorough review and after a substantial amendment has been approved by both competent authority and IEC.

3. Dose escalation to the highest dose group (70 mg tid) in the MRD part will not be done if the estimated systemic exposure (gMean $C_{max,ss}$ or $AUC_{0-24,ss}$) is expected to exceed the plasma exposure levels observed in the SRD part of the trial. In this case, the dose of the highest MRD dose group may be reduced to a dose >50 mg and <70 mg tid as long as the expected systemic exposure (gMean $C_{max,ss}$ and $AUC_{0-24,ss}$) is covered by the (preliminary) values measured in the SRD part ([Section 4.1.2](#)).

3.3.4.5 Discontinuation of a study part (SRD, MRD)

Dose escalation from an interim dose to the next planned dose level might be stopped, if the next dose level is not considered to contribute significantly to the PK analysis and the safety data set (e.g. if the dose difference is small).

If the SRD is stopped temporarily because criteria are met, the MRD will continue in the meantime.

3.3.5 Replacement of patients

In case that one dose group in this trial is completed by less than 6 patients on active treatment (due to e.g. drop-outs or recruitment reasons), the clinical trial leader together with the trial pharmacokineticist and the trial statistician are to decide if and how many patients will be replaced. A maximum of 3 patients can be replaced in each dose group (SRD and MRD). Only those patients will be replaced, which have not withdrawn due to adverse drug reactions or adverse events based on study procedures. A replacement patient will be assigned a unique patient number, and will be assigned to the same treatment as the patient he replaces.

4. TREATMENTS

4.1 INVESTIGATIONAL TREATMENTS

BI 894416 and placebo tablets.

4.1.1 Identity of the Investigational Medicinal Products

The characteristics of the test products are given below:

Table 4.1.1: 1 Test products

Substance:	BI 894416
Pharmaceutical formulation:	Tablet
Source:	Boehringer Ingelheim Pharma GmbH & Co. KG
Unit strength:	10 mg, 25 mg or 100 mg
Posology:	SRD part – single dose MRD part – tid dosing
Method and route of administration:	p.o.

The characteristics of the reference product (placebo) are given below:

Substance:	Placebo matching BI 894416 to match 10mg, 25mg and 100mg BI 894416 tablets
Pharmaceutical formulation:	Tablet
Source:	Boehringer Ingelheim Pharma GmbH & Co. KG
Unit strength:	0 mg
Posology:	SRD part- single dose MRD part – tid dosing
Method and route of administration:	p.o.

4.1.2 Selection of doses in the trial and dose modification

Maximum exposure (exposure cap)

The human exposure cap, which will be used to limit dosing, corresponds to a C_{max} gMean value of 5,233 nM and AUC_{0-24} gMean value of 36,150 nM·h, the latter corresponding to 3-fold below exposure at the dog NOAEL and 7-fold below the lowest exposure in dogs where neurologic effects were observed. In addition, predicted exposures above 63,000 nM·h will not be permitted for the 95th percentile of any given patient of the next dose group in this study. A neurological clinical examination assessment will be done in this trial at pre-defined time points (see [Flow Charts](#)). For more details on toxicology data supporting the selected human exposure cap, please see the current version of the Investigator's Brochure (IB) [[c03536505](#)].

Maximum dose

Maximum dose is described below, and this dose will not be exceeded in this trial. The doses selected for this trial cover the estimated therapeutic range and are expected to be necessary for successful development of BI 894416.

For the highest single dose in the SRD part, the C_{\max} gMean value is predicted to slightly exceed the upper limit of exposure (see [Table 4.1.2: 1](#) below). This dose will only be given if exposure (C_{\max}) at high doses is lower than currently predicted, i.e. the dose escalation stopping criterion referring to plasma exposure prediction is not reached (see [Section 3.3.4.4](#)) after single dose administration of up to 175 mg. Note: Before this trial, highest dose given to humans was 70 mg, i.e. predictions for doses higher than 70 mg are based on extrapolation and actual exposures may differ from predictions.

In case that preliminary PK analysis during the trial predict that exposure limit (see above) is exceeded with the highest SRD dose, the dose may be reduced to a dose > 175 and < 225 mg, as long as the predicted exposure at this reduced dose does not exceed the exposure limit.

In case the sponsor and SMC agree to test a dose level that is expected to exceed the maximal acceptable exposure defined above, this would only be done after approval of a substantial amendment by competent authority and IEC (according to [Section 7.5](#) of EMA guideline on strategies to identify and mitigate risks for first-in-human and early clinical trials with IMPs [[R18-1299](#)]).

Preliminary PK analysis

Dose escalation will be guided by preliminary PK analysis to ensure that the expected AUC and C_{\max} gMean values and the expected individual values (95th Percentile for AUC_{0-24}) for exposure at the next planned dose level do not exceed the maximum acceptable exposure.

Interim Dose Levels

With CTP version 3.0, an interim single dose group of 170 mg (SRD group 5) is added following dose group 2 (125 mg). Dose escalation to the next MRD dose group (dose group 3) may occur, as long as the expected systemic exposure (gMean $C_{\max,ss}$ and $AUC_{0-24,ss}$) is covered by the (preliminary) values measured in the interim SRD 5 dose group. See also [Section 3.1](#).

With CTP version 5.0, an interim multiple dose group of 60 mg tid (MRD group 5) is added following dose group 3 (50 mg tid). Dose escalation to the next MRD dose group (dose group 4) may occur, as long as the expected systemic exposure (gMean $C_{\max,ss}$ and $AUC_{0-24,ss}$) is covered by the (preliminary) values measured in the highest SRD dose group. See also Section 3.1.

SRD part

Table 4.1.2: 1 shows predicted PK parameters for single dose administration. Exposure multiples are calculated as a ratio of the maximal acceptable human exposure divided by predicted systemic exposure after single dosing.

Proprietary confidential information © 2020 Boehringer Ingelheim International GmbH or one or more of its affiliated companies

Table 4.1.2: 1 Predicted SRD PK parameters

Dosing Regimen [mg]	AUC ₀₋₂₄ [nM*h] (gMean)	Exposure multiple ¹	AUC ₀₋₂₄ [nM*h] (95th percentile)	Exposure multiple ²	C _{max} [nM] (gMean)	Exposure multiple ³
75 mg q.d.	12730	2.840	23262	2.708	1861	2.812
125 mg q.d.	21557	1.677	40152	1.569	3132	1.671
170 mg q.d.	29043	1.245	55171	1.142	4255	1.230
175 mg q.d.	29897	1.209	56794	1.109	4380	1.195
225 mg q.d.	38849	0.931	72987	0.863	5658	0.925

¹ in relation to AUC gMean exposure limit (36150 nM*h)

² in relation to 95th percentile exposure limit (63000 nM*h)

³ in relation to C_{max} gMean exposure limit (5233 nM)

The new interim dose 170 mg was inserted based on modelling from previous SRD part PK data.

Predicted PK parameters have been adapted for doses \geq 175 mg based on preliminary PK analysis including data from 75 mg and 125 mg dose groups.

Table 4.1.2: 2 SRD PK parameters obtained for doses up to 170 mg q.d.*

Dosing Regimen [mg]	gMean AUC ₀₋₂₄ [nM*h] (gCV [%])	gMean C _{max} [nM] (gCV [%])
75 mg q.d.	15200 (38.2)	2340 (29.7)
125 mg q.d.	25700 (29.9)	4128 (26.1)
170 mg q.d.	31700 (20.6)	5280 (24.3)

* Results from preliminary pharmacokinetic non-compartmental analysis

MRD part

Table 4.1.2: 2 shows predicted PK parameters for multiple dose administration. Exposure multiples are calculated as a ratio of the maximal acceptable human exposure divided by predicted systemic exposure after multiple dosing.

Table 4.1.2: 3 Predicted MRD PK parameters

Dosing Regimen [mg]	AUC _{0-24,ss} [nM*h] (gMean)	Exposure multiple ¹	AUC _{0-24,ss} [nM*h] (95th percentile)	Exposure multiple ²	C _{max,ss} [nM] (gMean)	Exposure multiple ³
10 mg t.i.d.	3691	9.794	6931	9.090	261	20.021
25 mg t.i.d.	13695	2.640	27453	2.295	960	5.450
50 mg t.i.d.	27577	1.311	52616	1.197	1929	2.712
60 mg t.i.d.	31727	1.139	61596	1.023	2241	2.335
70 mg t.i.d.	37732	0.958	72492	0.869	2648	1.977

¹ in relation to AUC gMean exposure limit (36150 nM*h)

² in relation to 95th percentile exposure limit (63000 nM*h)

³ in relation to C_{max} gMean exposure limit (5233 nM)

The new interim dose 60 mg tid was inserted based on modelling from previous MRD part PK data. Predicted PK parameters have been adapted for doses \geq 60 mg tid based on preliminary PK analysis including data from 10 mg tid, 25 mg tid and 50 mg tid dose groups.

The predicted exposure for 60 mg tid (AUC_{0-24,ss}) is 31727nM*h. The predicted exposure is covered by the exposure (AUC₀₋₂₄) obtained after administration of 170 mg q.d. (31700 nM*h). The difference of 27 nM*h is considered neglectable, taking the PK variability into consideration. In addition, the predicted exposure does not exceed the 95th percentile exposure limit for AUC_{0-24,ss} for 60 mg tid (61596 nM*h vs.63000 nM*h).

Table 4.1.2: 4 MRD PK parameters obtained for doses up to 50 mg t.i.d.*

Dosing Regimen [mg]	gMean AUC ₀₋₂₄ [nM*h] (gCV [%])	gMean C _{max} [nM] (gCV [%])
10 mg t.i.d.	4410 (48.6)	299 (42.7)
25 mg t.i.d.	14400 (19.8)	985 (19.4)
50 mg t.i.d.	16200 (33.5)	1290 (52.1)

* Results from preliminary pharmacokinetic non-compartmental analysis

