1.4.3.3 Summary of safety measures

The following precautionary measures will be taken in this study in order to minimise the risk for patients:

- Dose selection is based on safety, PK and [redacted] results of previous first-in-man trial 1371-0001, the mode of action, the expected pharmacologically active exposure, expected systemic exposures after single- and multiple-dose administration, and toxicity findings in preclinical studies. Escalation factor between dose steps decrease with increasing doses. For details see [Sections 4.1.2](#).
- A maximum acceptable human exposure has been defined for single and multiple-dose based on toxicity findings (see Section 4.1.2). Dose escalation is guided by preliminary analysis of BI 894416 PK (C_{max} and AUC_{0-24} for single dose; $C_{max,ss}$ $AUC_{0-24,ss}$ for multiple dose). The exposure in the next higher single-dose group will be predicted based on preliminary data of the current and preceding single dose groups and the exposure in the next higher multiple-dose group will be predicted based on preliminary data of the current and preceding single-dose and multiple dose groups. The next higher dose level will only be administered if
 1. predicted gMean value for AUC_{0-24} of the next dose group does not exceed the maximum acceptable human exposure of 36,150 nM*h (see Section 4.1.2),
 2. the upper limit of the 95% prediction interval for AUC_{0-24} of individual patients in the next dose group does not exceed 63,000 nM*h and 3) predicted gMean value for C_{max} of the next dose group does not exceed 5,233 nM.

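### Protocol Table 4.1.2:1 shows 175 mg under the Cmax cap at 4,380 nM, but the obtained data printed below it scale to 5,435–5,779 nM, over the 5,233 nM cap

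*Protocol*

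**What the plan says.** Protocol Section 4.1.2 sets three limits: geometric mean Cmax 5,233 nM, geometric mean AUC0-24 36,150 nM·h, and 63,000 nM·h for the 95th percentile of AUC0-24.

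Table 4.1.2:1 gives the single-dose predictions. Its 175 mg row reads "175 mg q.d. 29897 1.209 56794 1.109 4380 1.195", so all three exposure multiples are above 1. The note under the table says that predictions were adapted for doses at or above "175 mg based on preliminary PK analysis including data from 75 mg and 125 mg dose groups".

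Table 4.1.2:2 gives the values obtained so far, including "125 mg q.d. 25700 (29.9) 4128 (26.1" and "170 mg q.d. 31700 (20.6) 5280 (24.3" (geometric mean AUC0-24, then geometric mean Cmax, each followed by its gCV in per cent).

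For the top dose of 225 mg, the Cmax "gMean value is predicted to slightly exceed the upper limit of exposure". If the limit is predicted to be exceeded, "the dose may be reduced to a dose > 175 and < 225 mg", provided that the reduced dose is predicted to stay within the limit.

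The governing rule, Section 3.3.4.4 item 2, is predictive: "Dose escalation in the respective trial part will be stopped if the estimated systemic exposure of the next dose level is expected to exceed" the limits. Section 1.4.3.3 says what the prediction must use: "The exposure in the next higher single-dose group will be predicted based on preliminary data of the current and preceding single dose groups". Section 7.4 adds that all available data from this trial and from the healthy-volunteer trial are modelled, under a separate analysis plan.

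**The concern.** The two tables sit next to each other and do not agree. A larger dose is printed with a lower expected Cmax, and a lower expected AUC0-24 (29,897 against 31,700 nM·h), than a smaller dose has already produced. The rows for doses not yet given are described as updated, yet they show no sign of the higher exposure seen at 75 and 125 mg.

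The Cmax cap is one of three limits that control escalation. Table 4.1.2:1 is the dose justification that an ethics committee, an authority or a safety committee member would read. On its face, 175 mg has about 20% headroom and 225 mg only marginally fails. On the obtained data, 175 mg has no headroom and 225 mg is well over.

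**Working it through.** **Inputs.** Predictions are from Table 4.1.2:1, obtained values from Table 4.1.2:2, and limits from Section 4.1.2. Table 4.1.2:2 does not give group sizes. For the intervals I assume n = 8 actives (planned) and also show n = 6, the minimum for escalation.

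**The plan's own figure.** Multiple = cap / prediction. For Cmax at 175 mg: 5,233 / 4,380 = 1.195, as printed. All 15 multiples in the table reproduce, so the division is correct and the question is about the predictions.

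**Predicted against obtained Cmax (nM).**

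| Dose | Predicted | per mg | Obtained | per mg | Obtained/predicted |
|---|---|---|---|---|---|
| 75 mg | 1,861 | 24.8 | 2,340 | 31.2 | 1.26 |
| 125 mg | 3,132 | 25.1 | 4,128 | 33.0 | 1.32 |
| 170 mg | 4,255 | 25.0 | 5,280 | 31.1 | 1.24 |
| 175 mg | 4,380 | 25.0 | – | – | – |
| 225 mg | 5,658 | 25.1 | – | – | – |

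The adapted rows lie on the same line as the others. For AUC0-24 the ratios are 15,200/12,730 = 1.19, 25,700/21,557 = 1.19 and 31,700/29,043 = 1.09.

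**Is the Cmax gap noise?** With s² = ln(1 + gCV²) and gCV 29.7%, 26.1% and 24.3%, the mean log ratio is 0.240. Its standard error is √(Σs²/n)/3 = 0.0537 for n = 8. The pooled ratio is 1.27, with 90% CI 1.16–1.39 (n = 8) or 1.14–1.42 (n = 6). The shared under-prediction is not sampling error.

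**Scaling to 175 mg.** The log-log slope of the three obtained means is 1.006, so proportional scaling is reasonable.
- From 75 mg: 2,340 × 175/75 = 5,460 nM, multiple 0.96.
- From 125 mg: 4,128 × 175/125 = 5,779 nM, multiple 0.91.
- From 170 mg: 5,280 × 175/170 = 5,435 nM, multiple 0.96.
- From 75 and 125 mg only, the data named in the note: 32.10 nM/mg × 175 = 5,617 nM.
- Pooled over three groups: 31.75 nM/mg × 175 = 5,556 nM, 90% CI 5,065–6,094 (n = 8) or 4,983–6,194 (n = 6).

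Every point estimate is over 5,233 nM. The pooled interval includes the cap but excludes the printed 4,380.

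**Scaling to 225 mg.** The results are 7,020, 7,430 and 6,988 nM, or 34–42% over the cap. The printed excess is 5,658/5,233 = 1.081, or 8.1%. The pooled value is 7,143 nM (90% CI 6,513–7,835, n = 8), wholly above the cap.

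**Dose at the cap.** On the printed line: 5,233 × 175/4,380 = 209 mg. On the obtained data: 5,233/31.75 = 165 mg, below a dose already given.

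**AUC0-24 at 175 mg.** 15,200 × 175/75 = 35,467; 25,700 × 175/125 = 35,980; 31,700 × 175/170 = 32,632 nM·h. All are under 36,150. I have not recomputed the 95th percentile limit, because it depends on the sponsor's model.

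**The case against.** The strongest reply is that the table does not decide anything. For 175 mg the current group is 170 mg, so Section 1.4.3.3 requires the 170 mg data to enter the prediction, and Section 7.4 requires modelling of everything available. A refit consistent with the obtained values puts 175 mg over the cap, and Section 3.3.4.4 item 2 then stops escalation. This stands, and it limits the weight of the point.

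A reader might infer that the protocol would have let 175 mg through, or that it lacks a necessary stop on obtained exposure. The documents do not support that. The limits are written on predicted exposure, but a rising dose-exposure relation carries an obtained excess into the next prediction. A reader might also infer that the stop after 170 mg rested on the team's discretion. SAP Section 6.1 instead attributes it to the exposure limits in the protocol being reached, and records that 175 and 225 mg were not performed.

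Other replies hold in part. The 75, 125 and 170 mg rows are forecasts, and Section 4.1.2 warns that figures above 70 mg are extrapolations; missing a forecast is not an error in itself. The model also includes healthy-volunteer data and need not pass through preliminary non-compartmental means. But neither reply explains why rows described as adapted with patient data keep the same nM per mg, or why 175 mg is printed 17% below what 170 mg delivered. The 225 mg row already fails all three limits, and Section 4.1.2 permits that dose only if Cmax proves lower than predicted. Correcting its size therefore changes the description, not the decision.

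**Conclusion.** The point holds as a defect in the printed dose justification. The 175 and 225 mg rows are not reconciled with the obtained Cmax, including the 75 and 125 mg data that they cite. The 175 mg row shows a pass where the obtained data give a fail by 3.9–10.4% on Cmax, and *slightly* understates a 225 mg excess of 34–42%. The geometric mean AUC limit is still met at 175 mg.

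This rests on dose proportionality, which the three obtained means support, and on preliminary PK values. Group size affects only the intervals. The documents do not show the model, so I cannot say whether the rows were left unrefreshed or the refit barely moved them.

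A reader might take the 170 mg result as a breach of the cap. It is 47 nM (0.9%) over, with 90% CI 4,497–6,199 nM at n = 8, so the true mean may lie on either side. The cap also acts through predictions. No dosing harm followed. Severity is minor to moderate.

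**What to change.** 1. Recompute the 175 and 225 mg rows of Table 4.1.2:1 so that they are consistent with the 75, 125 and 170 mg data, and name the data used.
2. In the maximum-dose text, replace *slightly* with the recomputed excess.
3. Mark 175 mg, and the window above 175 and below 225 mg, as not available unless the recomputed values meet all three limits.
4. Show obtained/predicted ratios for Cmax and AUC0-24 for every completed group at each safety review.

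The cost is one protocol amendment and one short table per review. As 175 and 225 mg were not given, items 1–3 now serve mainly to leave a correct record.

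An explicit stop when a completed group's obtained mean exceeds a limit is optional. It would be simple to apply but would sometimes trip by chance. With gCV 24.3% and n = 8 (standard error 0.0847 on the log scale), a group whose true mean Cmax is 10% below the cap would trigger it about 11% of the time, and one 5% below about 27%. If adopted, it should require a substantial amendment before any higher dose rather than end the part.
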